SD	Preliminary PR	Yes or No	Stable/Better	Any	Stable/Decreasing	SD (preliminary PR → confirmed PR)
SD	Preliminary CR	Yes or No	Stable/Better	Any	Stable/Decreasing	SD (preliminary CR → confirmed CR)
CR	Preliminary CR	No	Stable/Better	No	N/A	Confirmed CR
SD	Preliminary PD	No	Stable/Better	Any	Stable/Decreasing	SD (Confirmed PsP)
CR/PR/SD /PD/NE	CR/PR/SD/PD /NE	Yes or No	Worse	Any	Stable/Increasing	Confirmed PD
PD	Preliminary PD	Yes or No	Any	Yes	Stable/Increasing	Confirmed PD

a. Note that new sites of measurable disease are added to the sum of bidimensional products or total lesion volume, or constitutes preliminary PD in the case of no measurable disease at baseline or best response.

Baseline Assessments for Newly Diagnosed GBM

Newly diagnosed GBM patients will usually undergo an MRI scan for initial diagnosis prior to entry in the study and prior to therapy. The post-operative scan is desired in order to assess residual enhancing disease volume for use as a covariate in survival analyses, as described previously. Patients will then start on standard or experimental therapy with concurrent radiation therapy (RT).

The Post-RT scan should be used as the baseline scan for which response and disease progression will be determined. Following the first cycles of adjuvant therapy, patients will receive additional required MRI scans.

Details Common to Both Newly Diagnosed and Recurrent GBM

Preliminary Radiographic Progression. If the lesion size has increased $\geq 25\%$ sum of bidirectional product or $\geq 40\%$ in volume between MRI Scan 1 and N, these patients should be categorized as "preliminary radiographic progression." If the investigator believes the patient can safely continue on therapy, then they should continue to treat and acquire a follow-up confirmatory scan [MRI(N + 1)] at the next scan interval (8 weeks \pm 4 weeks from MRI Scan (N) or no less than 4 weeks minimum duration between preliminary PD and confirmed PD scans) to verify tumor growth and progression. For patients with gross-total resection (GTR) and no measurable enhancing disease, preliminary radiographic progression is defined as a transition from no measurable disease to nonmeasurable (but present) disease ($< 10 \text{ mm} \times 10 \text{ mm}$) or measurable disease ($> 10 \text{ mm} \times 10 \text{ mm}$). If the investigator feels it is safe to keep the patient on, a confirmatory scan at MRI(N + 1) should be obtained to verify tumor progression.

Confirmed Progression. If the patient has an increase $\geq 25\%$ sum of bidirectional product or $\geq 40\%$ in volume between MRI Scan N and N + 1, this is "Confirmed Progression," the patient should stop therapy and the date of radiographic progression is the date of suspected progression, MRI(N). If the patient has SD/PR/CR on MRI(N + 1) with respect to MRI(N), PsP is confirmed and the patient should continue on therapy. Patients will then continue on therapy and receive additional follow-up MRI scans [MRI(M)]. If the lesion size has increased $\geq 25\%$ sum of bidirectional product or $\geq 40\%$ in volume on MRI(M) relative to the smaller of Nadir or MRI(N + 1), then the patient has "Confirmed Progression," the patient should stop therapy (unless otherwise allowed per protocol) and the date of radiographic progression is the new date, MRI(M). For patients with no measurable disease at the Post-RT baseline, "Confirmed Progression" will be defined as a transition from non-measurable (but present) disease ($< 10 \text{ mm} \times 10 \text{ mm}$) on MRI(N) to measurable disease ($> 10 \text{ mm} \times 10 \text{ mm}$) on MRI(N + 1). For patients with confirmed PsP and no measurable disease at Nadir, "Confirmed Progression" should be defined as a transition from no measurable disease to measurable disease ($> 10 \text{ mm} \times 10 \text{ mm}$). In all cases, patients with confirmed progression should stop therapy.

[figure not shown]
Preliminary & Confirmed Radiographic Response. If a measurable lesion has decreased $\geq 50\%$ sum of bidirectional product or $\geq 65\%$ in volume between MRI(1) and MRI(N), these patients should be categorized as "preliminary radiographic responders" and will be monitored for an additional time point and/or treatment cycle. After an additional cycle of therapy (8 weeks \pm 4 weeks from MRI(N)), patients will receive a confirmatory MRI(N + 1). If the lesion(s) have increased $\geq 25\%$ sum of bidirectional product or $\geq 40\%$ in volume from MRI(N) (indicating radiographic progression from MRI(N)), this is considered an "unsustained radiographic response" or "pseudoresponse." The date of radiographic progression for these patients will be MRI(N + 1) and the patient should stop therapy. Alternatively, if the lesion has not increased from MRI(N), this is considered a "durable radiographic response," the patient will continue on therapy, and the date of preliminary radiographic progression is the time point of an increase $\geq 25\%$ sum of bidirectional product or $\geq 40\%$ in volume (from Nadir) during the remainder of the study. The investigator can then decide whether to continue safely on therapy until progression has been confirmed and at the subsequent time point stop therapy if they feel the patient cannot safely continue therapy.

Stable Disease. If the lesion size has not increased or decreased beyond the set thresholds between Scan 1 and N, the patient is considered "stable." Such patients will continue on therapy, and the date of preliminary progression is the time point of an increase $\geq 25\%$ sum of bidirectional product or $\geq 40\%$ in

volume (from Nadir) during the remainder of the study. Upon preliminary progression the investigator can choose to either continue therapy and confirm progression or discontinue therapy. For cases with significant neurologic decline at the time of imaging progression as determined from MRI(N), a confirmatory scan at time point MRI(N + 1) may not be possible or necessary. For these cases, it is appropriate to define MRI(N) as the progression time point.

Open Access. The guidelines provided for this study protocol are adapted, with protocol-specific clarifications, from Ellingson et al (2017). The original was distributed under the terms of the Creative Commons Attribution 4.0 International License (<http://creativecommons.org/licenses/by/4.0/>), which permits unrestricted use, distribution, and reproduction in any medium, provided that the user gives appropriate credit to the original author(s) and the source, provides a link to the Creative Commons license, and indicates if changes were made.

Figure 1. Radiographic Response Assessment Rubric for Newly Diagnosed Glioblastoma

GBM = glioblastoma; MRI = magnetic resonance imaging; PD = progressive disease; PR = partial response; PsP = pseudoprogression; RT = radiation; SD = stable disease; Tx = treatment; wrt = with regard to

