During the Adjuvant Phase, all subjects will receive oral TMZ (150 – 200 mg/m²) once daily, on Days 1 – 5 of each 28-day cycle, for 6 – 12 cycles, depending on local standard of care. All subjects will receive depatuxizumab mafodotin at 1.25 mg/kg IV infusion once every 2 weeks (on Day 1 and Day 15 of each 28-day cycle) for 12 cycles. Adjuvant treatment will be discontinued upon determination of tumor progression as defined by Response Assessment in Neuro-Oncology Working Group (RANO) criteria (Operations Manual, Appendix I), unacceptable toxicity, or refusal to continue study treatment.

Subjects will be randomized to 1 of 3 prophylactic eye treatment arms (1:1:1), to be administered with each infusion of depatuxizumab mafodotin (during both Chemoradiation Phase and Adjuvant Phase):

- Arm A (SS) – Standard Steroids
- Arm B (SS/VC) – Standard Steroids + Vasoconstrictor + Cold Compress
- Arm C (ES/VC) – Enhanced Steroids + Vasoconstrictor + Cold Compress

Subjects will be monitored at regular intervals for OSEs by AE reports and by ophthalmology examinations (including slit lamp examination and visual acuity testing).

[figure not shown]
For subjects who demonstrate inadequate control of OSEs with the initial prophylactic strategy, according to predefined criteria for loss of visual acuity and/or OSE symptom severity, intervention with a BCL will first be employed (Figure 2). Subjects who continue to demonstrate inadequate response to BCL intervention (CEAE Grade 3 or higher OSE symptom severity) will be eligible for unrestricted OSE management according to investigator discretion. In this case, depatuxizumab mafodotin dose interruption and/or reduction may be used, and any available prophylactic (including addition of ES and VC regimens if not used initially) or supportive care measures may be employed without restriction, at the discretion of the investigator.

Subjects who complete 8 weeks of adjuvant therapy (8 weeks after the first dose of adjuvant depatuxizumab mafodotin) will be allowed to enter the Investigator Discretion phase regardless of CEAE Grade, visual acuity or BCL intervention.

Visual acuity will be measured using the LogMAR scale for visual acuity, while OSE symptom severity will be measured by the Corneal Epithelial AE grading scale (see Section 6.1 and Operations Manual, Section 4.3), which was developed by the sponsor for assessing and managing corneal epitheliopathy associated with ADCs.

[figure not shown]

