Radiographic response should be determined in comparison to the tumor measurements obtained at baseline (post-radiation scan will be baseline for newly diagnosed GBM, and pretreatment scans will be the baseline for recurrent GBM) for determination of response, and the smallest tumor measurement at either pre-treatment baseline or following initiation of therapy for determining progression.

Because novel treatments are likely to result in a higher than normal incidence of treatment-related increase in contrast enhancement ("pseudoprogression," PsP) or decrease in contrast enhancement ("pseudoresponse," PsR), patients should continue therapy with close observation (e.g., 4 – 8 week intervals) if there is a suspicion of PsP or PsR. If subsequent imaging studies and/or clinical observations demonstrate that progression in fact has occurred, the date of confirmed progression should be noted as the scan at which the potential progression was first identified. Definitions for complete response, partial response, progressive disease, and stable disease should be defined as follows for all target lesions.

Complete Response (CR): Requires all of the following:

1. Disappearance of all enhancing measurable and nonmeasurable disease sustained for at least 4 weeks. The first scan exhibiting disappearance of all enhancing measurable and non-measurable disease is considered "preliminary CR." If the second scan exhibits measurable

enhancing disease with respect to the "preliminary CR" scan, then the response is not sustained, noted as pseudoresponse, PsR, and is now considered "preliminary PD" (note confirmed PD requires at least two sequential increases in tumor volume). If the second scan continues to exhibit disappearance of enhancing disease or emergence of non-measurable disease (less than 10 mm bidimensional product), it is considered a durable CR and the patient should continue on therapy until confirmed PD is observed.

2. Patients must be off corticosteroids (or on physiologic replacement doses only).
3. Stable or improved clinical assessments (i.e., neurological examinations).

Note: Patients with non-measurable disease only at baseline cannot have CR; the best response possible is stable disease (SD). (For the current study subjects without measurable disease at baseline are ineligible for study entry.)

Partial Response (PR): Requires all of the following:

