1. $\geq 50\%$ decrease in sum of products of perpendicular diameters or $\geq 65\%$ decrease in total volume of all measurable enhancing lesions compared with baseline, sustained for at least 4 weeks. The first scan exhibiting $\geq 50\%$ decrease in sum of products of perpendicular diameters or $\geq 65\%$ decrease in total volume of all measurable enhancing lesions compared with baseline is considered "preliminary PR." If the second scan exhibits PD with respect to the "preliminary PR" scan, then the response is not sustained, noted as pseudoresponse, PsR, and is now considered "preliminary PD" (note confirmed PD requires at least two sequential increases in tumor volume). If the second scan exhibits SD, PR, or CR, it is considered a durable PR and the patient should continue on therapy until confirmed PD is observed.
2. Steroid dose should be the same or lower compared with baseline scan.
3. Stable or improved clinical assessments.

Note: Patients with non-measurable disease only at baseline cannot have PR; the best response possible is stable disease (SD). (For the current study subjects without measurable disease at baseline are ineligible for study entry.)

Progressive Disease (PD): Defined by any of the following:

1. At least two sequential scans separated by at ≥ 4 weeks both exhibiting $\geq 25\%$ increase in sum of products of perpendicular diameters or $\geq 40\%$ increase in total volume of enhancing lesions. The first scan exhibiting $\geq 25\%$ increase in sum of products of perpendicular diameters or $\geq 40\%$ increase in total volume of enhancing lesions should be compared to the smallest tumor measurement obtained either at baseline (if no decrease) or best response (on stable or increasing steroid dose) and is noted as "preliminary PD." If the second scan at least 4 weeks later exhibits a subsequent $\geq 25\%$ increase in sum of products of perpendicular diameters or $\geq 40\%$ increase in total volume of enhancing lesions relative to the "preliminary PD" scan, it is considered "confirmed PD" and the patient should discontinue therapy. If the second scan at least 4 weeks later exhibits SD or PR/CR, this scan showing "preliminary PD" is noted as "pseudoprogression," PsP, and the patient should continue on therapy until a second increase in tumor size relative to the PsP scan is observed. Note that any new measurable (> 10 mm \times

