10 mm) enhancing lesions should not be immediately considered PD, but instead should be added to the sum of bidimensional products or total volume representing the entire enhancing tumor burden.

2. In the case where the baseline or best response demonstrates no measurable enhancing disease (visible or not visible), then any new measurable (> 10 mm × 10 mm) enhancing lesions are considered PD after confirmed by a subsequent scan ≥ 4 weeks exhibiting ≥ 25% increase in sum of products of perpendicular diameters or ≥ 40% increase in total volume of enhancing lesions relative to the scan first illustrating new measurable disease. The first scan exhibiting new measurable disease is noted as "preliminary PD." If the second scan at least 4 weeks later exhibits a subsequent ≥ 25% increase in sum of products of perpendicular diameters or ≥ 40% increase in total volume of enhancing lesions relative to the "preliminary PD" scan it is considered "confirmed PD" and the patient should discontinue therapy. If the second scan at least 4 weeks later exhibits SD, CR, PR, or becomes non-measurable, this scan showing "preliminary PD" is noted as "pseudoprogression," PsP, and the patient should continue on therapy until a second increase in tumor size relative to the "preliminary PD," or PsP, scan is observed. Note that any new measurable (> 10 mm × 10 mm) enhancing lesions on the subsequent scan following the preliminary PD scan should not be immediately considered confirmed PD, but instead should be added to the sum of bidimensional products or total volume representing the entire enhancing tumor burden.
3. Clear clinical deterioration not attributable to other causes apart from tumor (e.g., seizures, medication adverse effects, therapy complications, stroke, infection) or attributable to changes in steroid dose.
4. Failure to return for evaluation as a result of death or deteriorating condition.

Stable Disease (SD): Requires all of the following:

1. Does not qualify for CR, PR, or PD as defined above. Note this also applies to patients that demonstrate PsR when the confirmation scan does not show PD or PsP when the confirmation scan does not show PR/CR.

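### Operations Manual Appendix I carries two sets of progression rules that give opposite continue/stop instructions for the same scans

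*Protocol*

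**What the plan says.** Appendix I of the Operations Manual has a definitions part (complete response, partial response, progressive and stable disease, summarised in Table 2) and a rubric part (preliminary and confirmed progression, radiographic response, stable disease).

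**After confirmed pseudoprogression.** Progressive Disease item 1 says "the patient should continue on therapy until a second increase in tumor size relative to the PsP scan is observed". Item 2 makes clear that the PsP scan is the one that first showed preliminary progression, MRI(N). The rubric paragraph on confirmed progression instead says that if a later scan shows a 25% or 40% increase "relative to the smaller of Nadir or MRI(N + 1), then the patient has" confirmed progression and should stop.

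**Regrowth after a preliminary response.** The complete and partial response definitions class the regrowth scan as preliminary progression only, with the reminder "note confirmed PD requires at least two sequential increases in tumor volume". Table 2 gives the same status. The rubric says of the same scan: "The date of radiographic progression for these patients will be MRI(N + 1) and the patient should stop therapy".

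**No measurable disease.** Progressive Disease item 2 makes the first measurable lesion preliminary progression and requires a further 25% or 40% increase at least 4 weeks later. The rubric begins earlier: "For patients with gross-total resection (GTR) and no measurable enhancing disease, preliminary radiographic progression is defined as a transition from no measurable disease" to a lesion that is present but still too small to measure, or to a measurable one. It then treats the step from non-measurable on MRI(N) to measurable on MRI(N + 1) as confirmed progression.

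**Eligibility.** Notes under both response definitions state: "For the current study subjects without measurable disease at baseline are ineligible for study entry". Protocol 5.1 has no such criterion. Appendix I takes the post-radiation scan as baseline, and SAP 8.1 lists gross total resection as a surgery category.

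**Link to treatment.** Protocol 4.1 says "Adjuvant treatment will be discontinued upon determination of tumor progression" by the Appendix I criteria. Protocol 5.5 makes confirmed progression a mandatory reason for withdrawal. Protocol Appendix E lets continuing subjects be dosed only while progression has not been determined.

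**The concern.** Progression is called by the investigator (Protocol 7.3) on imaging done to local standard (Operations Manual 3.17), so each site applies Appendix I for itself. If two paragraphs classify one scan series differently, similar subjects can be stopped at one site and continued at another. The last-dose date then feeds analyses that the abbreviated SAP keeps: cumulative dose (5.3.2, 9.2), treatment duration (9.2), reasons for discontinuation (9.1), and the 49-day limit on treatment-emergent events and on censoring of time to first corneal event (7.3, 11.2, 11.4).

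**Working it through.** The point depends on no sample size, power or error rate. The check applies each pair of rules to one scan series. Scan values are assumed for illustration; thresholds come from Appendix I Table 1.

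**Thresholds.** If volume scales as the bidimensional product to the power 1.5, then 1.25^1.5 − 1 = 39.8% (Table 1: 40%) and 1 − 0.5^1.5 = 64.6% (Table 1: 65%). The thresholds are consistent; the conflict lies in the reference scan and in the need for confirmation.

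**Situation 1: after pseudoprogression.** Products: nadir 400, MRI(N) 600, MRI(N + 1) 450, MRI(M) 580.
- 600/400 − 1 = +50%: preliminary progression.
- 450/600 − 1 = −25%: stable relative to MRI(N), so pseudoprogression.
- Definitions: 580/600 − 1 = −3%. No increase over the PsP scan, so continue.
- Rubric: the smaller of 400 and 450 is 400, and 580/400 − 1 = +45%. Confirmed progression, so stop.
- The rubric stops from 1.25 × 400 = 500. The definitions continue at least up to 600. The two therefore disagree for any MRI(M) from 500 to 600.

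The split does not depend on these values. The series 400, 520, 390, 500 gives −3.8% against +28.2%. The volumes 10, 14.5, 10, 14.2 give −2.1% against +42%.

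**Situation 2: regrowth after preliminary response.** Products: 1000, 450, 600.
- 450/1000 − 1 = −55%: preliminary partial response.
- 600/450 − 1 = +33%.
- Definitions and Table 2: preliminary progression, with a further increase needed.
- Rubric: progression dated at this scan, stop.

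**Situation 3: no measurable disease.** MRI(N) shows an 8 × 8 mm lesion and MRI(N + 1) a 12 × 12 mm lesion (144 mm²).
- Definitions: MRI(N + 1) is the first measurable scan, hence preliminary progression. Confirmation needs at least 1.25 × 144 = 180 mm² on a later scan.
- Rubric: MRI(N) was already preliminary and MRI(N + 1) confirms it, so stop.

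**Effect on exposure.** In situations 2 and 3, assume the subject continues at the planned adjuvant dose until one confirmatory scan, at the rubric's interval of 8 ± 4 weeks. Infusions are every 2 weeks at 1.25 mg/kg.
- Extra infusions: 4/2 = 2 to 12/2 = 6.
- Extra cumulative dose: 2 × 1.25 = 2.5 to 6 × 1.25 = 7.5 mg/kg, against a planned adjuvant total of 24 × 1.25 = 30 mg/kg.

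This is a difference in stopping time. For situation 1 the documents give no interval that bounds the delay.

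**Effect on the primary endpoint.** It covers 8 weeks from first dose. Operations Manual Appendix A places MRI(N) after the first adjuvant cycle, so on planned timings at about 6 + 4 + 4 = 14 weeks.

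**The case against.** The best defence is that Appendix I points to the rubric. The introduction to the rubric says that modified rubrics are to be used for treating beyond suspected progression and for defining progression. The definitions' own general sentence also measures progression from the smallest measurement, which agrees with the rubric in situation 1. This narrows the conflict but does not settle it. Nothing says that the definitions or Table 2 give way, and both continue to issue their own statuses and instructions. The rubric figure is not reproduced in the text available here, so whether it settles anything cannot be judged.

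Appendix I also opens by limiting RANO to determining PFS and says that response need not be recorded. Situation 2 may therefore arise less often in practice. Protocol 4.1 and 5.5 nevertheless use the same appendix to stop treatment and withdraw subjects. The rubric's stop after pseudoprogression carries an exception for what the protocol otherwise allows, but the same paragraph closes by requiring a stop in all cases of confirmed progression.

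A reader might infer four stronger points, none of which the documents support:
- *After pseudoprogression the lesion must reach 1.25 × 600 = 750 before the definitions stop treatment.* The sentence gives no percentage; read literally, anything above 600 suffices.
- *Progression dates shift by 4 to 12 weeks.* In situation 2 the definitions back-date confirmed progression to the scan where it was first suspected, which is the scan the rubric uses. If progression is later confirmed, the dates agree and only the stopping time differs. In situation 1 the interval for confirming preliminary progression does not measure the gap.
- *Ocular follow-up is lost when a subject stops.* Protocol 4.1 and 5.6 continue it until resolution after discontinuation for any reason.
- *Completely resected patients were shut out.* Operations Manual 3.4 refers eligibility to Protocol 5.1, the screening list has no MRI, the baseline scan follows entry, and enrolment has closed at 40. The notes are a textual conflict; there is no sign that they acted as an exclusion.

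**Conclusion.** Wrong as written, with low-to-moderate severity. In each of the three situations the current text supports both continuing and stopping on identical scans, and no clause says which part prevails. The eligibility notes are a fourth inconsistency.

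The practical consequence is that adjuvant exposure and cumulative dose can depend on the paragraph used. This affects an unknown number of at most 40 subjects. The 2 to 6 infusions apply to situations 2 and 3 only and rest on one confirmatory interval, uninterrupted planned dosing and an investigator who elects to continue.

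The statistical damage is limited. The primary endpoint window closes before these follow-up scans are due, and SAP 10.0 analyses no efficacy endpoint, so no planned PFS result is distorted.

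**What to change.** Reconcile the definitions, Table 2 and the rubric text of Appendix I so that each states the same single rule for:

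1. the reference scan, and the size of increase required, after confirmed pseudoprogression;
2. regrowth after a preliminary response;
3. preliminary and confirmed progression when there is no measurable disease.

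Reconcile the two eligibility notes with Protocol 5.1 and with the post-radiation baseline. Which rule applies in each case is the sponsor's clinical decision.

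The cost is a wording change and a short clarification to sites, with no new scans or readers. Since the Operations Manual is Protocol Appendix G, the change may need the amendment review described in Protocol 8.1.
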